3. SYNOPSIS

Title of Study	Transatlantic Registry of Type A Aortic Dissection (TARTAAD)		
Sponsor	University Hospital of Helsinki (Finland)		
Study	Primary Hypothesis: understanding the patient's conditions and		
Hypothesis	treatment strategies which are associated with postoperative		
	outcomes is essential for an appropriate management of acute TAAD		
Study	Primary objective: to identify the predictors influencing early and late mortality		
Objectives	in TAAD patients undergoing open heart surgery		
	• Secondary objectives: to elucidate and identify predictors of: 1) re-		
	exploration for bleeding; 2) cerebrovascular accident 3) surgical site infection;		
	4) blood transfusion; 5) acute kidney injury; 6) length of intensive care unit		
	(ICU) stay; 7) length of hospital stay and 8)		
	reoperation after hospital discharge; 8) late survival; 9) rate of late re-intervention.		
Study Design	Retrospective observational cohort study registry		
Planned Sample	This study will use data from 32 high-volume aortic centers.		
Size	It is anticipated that the final database will approximately contain clinical		
Culain at	details for more than 10000 patients.		
Subject	Inclusion criteria:		
Selection Criteria	• Type A aortic dissection or intramural hematoma involving the aortic		
Criteria	root/ascending aorta; • Patients aged > 18 years: • Symptoms started within 7 days from surgery; • Primary surgical repair of acute type A aortic dissection;		
	Any other major cardiac surgical procedure		
	concomitant with surgery for type A aortic dissection		
Intervention	This is a non-interventional study		
Study period	1 January 2010 – 31 December 2024		
Follow-up/End-	31 December 2025		
study			
Primary	Mortality rate during the index hospital stay until last follow-up control		
Outcomes	Cumulative incidence of reoperation on the aorta during the index hospital		
	stay until last follow-up control (any surgical and endovascular procedure on		
	any segment of the aorta for aortic dissection or its		
0	related complication)		
Secondary	1) Incidence of stroke; 2) Incidence of acute kidney injury; 3) Incidence of		
Outcomes	surgical site infection; 4) Incidence of reoperation for bleeding; 5) Incidence		
	and amount of blood transfusion; 6) Length of stay in the intensive care unit; 7) Incidence of global brain ischemia; 8) Incidence of paraplegia/paraparesis; 8)		
	late survival; 9) rate of late re-intervention		
	late salvival, syrate of late to intervention		

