5. BACKGROUND AND RATIONALE

5.1. Background

Acute Stanford type A aortic dissection (TAAD) is a life-threatening condition. Surgery is usually performed as a salvage procedure and is associated with increased postoperative early mortality and morbidity (1). Although early mortality has declined during the last years (2), the recent The Nordic Consortium for Acute Type A Aortic Dissection registry including 1189 patients operated from 2005 to 2015 in 8 centers showed that 30-day mortality after surgery for acute TAAD was 18% (3). The multicentre, prospective German Registry for Acute Aortic Dissection Type A including 2137 TAAD patients operated from 2006 and 2010 documented a 30-day mortality of 16.9% (4). A more recent analysis of the Society of Thoracic Surgeon database including 7353 patients operated from 2014 and 2017 for acute TAAD reported a 30-day mortality of 17% (5). Furthermore, surgery for TAAD is often complicated by major adverse events such as stroke (5) and acute kidney failure (6), which may have a significant impact on late survival. In this scenario of significant postoperative mortality and morbidity, surgeon faces the controversial issue of the extent of surgical repair for acute TAAD by avoiding a major surgical repair with its possible increased risk of early adverse event. At the same time, the surgeon would need to decide on whether to resect aortic segments which may expose the patient to the risk of late complications at the level of the aortic root (7) as well as of the aortic arch or distal to it (8). Understanding the balance between the patient's conditions which may not allow extensive procedure and those treatment strategies which may limit the risk of late adverse events in patients who remain alive long after the surgery is essential for an appropriate management of TAAD. We aim to create the present multicenter European registry of surgery for acute TAAD (ERTAAD) to evaluate the contemporary early outcomes and late durability of different surgical strategies for acute TAAD in a large study population within a long follow-up period.

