8.1. Number of Participants

An estimated number of 20-25 patients affected by TAAD and undergoing open heart surgery are usually admitted in mid/high-volume aortic centres (1). Therefore, it is estimated that the registry will encompass more than 5000 patients in total. Locally, the number of patients admitted to Glenfield Hospital (University Hospitals of Leicester NHS Trust) fulfilling the inclusion criteria between 1 January 2010 and 31 December 2025 is (average) 15-20 per year.

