8.2. Sample Size Calculation

The impact of total aortic arch repair compared to more limited aortic resection on the early and late outcomes will be one of the main topics of research from this registry. Therefore, in the light of the expected limited frequency of this surgical strategy, we performed a sample size analysis considering the extent of distal aortic resection. Despite the limitation of a pooled analysis which did not take in to account the cumulative incidences from competing risk analysis and the segment of repeat operation, Poon et al. (24) estimated a pooled hazard ratio on 0.73 (95%CI 0.56-1.18) of freedom from any late aortic reoperation for total arch replacement. Based on this hazard ratio, a sample size of 163 patients per study groups would be enough to reject the null hypothesis (alpha 0.05, power 0.80). Pan et al. (25) reported a freedom from distal reoperation after ascending aortic resection at 8 years of 95.3% which was not statistically different from that of hemiarch or total aortic arch repair (92.4%, p=0.22). For the sample size calculation of a non-inferiority trial, we assumed a freedom rate from distal aortic reoperation of 95% and we considered that a difference in the reoperation rate as large as 10% in favor of a total aortic arch repair still allow the less extensive repair to be non-inferior (delta=0.1, power 0.90, one-sided confidence 97.5%), the required sample size would be 100 patients per each group. We assume that about 5% of patients have undergone total arch repair in this collaborative registry and therefore a study population of 4000 patients would be enough to investigate the impact of total aortic arch repair in preventing late aortic reoperation in patients with acute TAAD.

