8.3. Statistical Analysis

Statistical analyses will be conducted using Stata v. 15.1 (StataCorp LLC, Texas, USA) and SPSS v. 29.0 (IBM Corporation, Armonk, NY, USA) statistical softwares. Continuous variables and outcomes will be summarized as mean and standard deviation as well as median and interquartile range. Categorical variables and outcomes will be reported as counts and percentages. A p<0.05 will be set for statistical significance. Differences between the study groups will be evaluated using the Fisher's exact test, the Chi-square test, the linear-by-linear association test, the Mann-Whitney test and the Kruskal-Wallis test. The McNemar test and paired samples T-test will be used in case of

analysis of paired groups. Propensity score matching will be performed to balance treatment strategies for baseline differences. A propensity score will be estimated using a non-parsimonious multilevel mixed-effects logistic regression considering the cluster effect of the participating centers whose results may be affected by the referral pathway, surgical techniques and perioperative care. Multilevel mixed-effects logistic regression model will include all available baseline variables. One-to-one propensity score matching will be performed using a caliper width of 0.2 of the standard deviation of the estimated logit. Standardized differences <0.10 will be considered an acceptable imbalance between the matched cohorts. The estimated propensity score will be also included into regression models to adjust for multiple confounders or for analysis within its strata.

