Logistic and linear regression analyses will be employed to identify independent risk factors for early adverse events with and without a stepwise approach. For the purpose of developing a risk scoring method from this registry, the study cohort will be randomly divided into two datasets, i.e. the derivation data set (75.0% of patients) and the validation data set (25.0% of patients). Univariate analysis will be performed on all candidate covariates of the derivation dataset to identify predictors of in-hospital mortality. Multiple logistic regression analysis will be then performed using the derivation dataset. A stepwise procedure with a bootstrap approach will be used, and 100 samples will be extracted with a size of 70% of the derivation dataset. A stepwise procedure will be applied to each sample (probability to stay = 0.05; probability to entry = 0.1). Variables selected in at least 50% of the stepwise procedures will be included in the regression model. Additional covariates were selected using a forward selection comparing the Akaike information criterion for the models with and without each covariate. The model with the lowest Akaike information criterion will be selected for each forward step, until the inclusion of a new covariate determined an increase in the Akaike information criterion value. The model will be tested in the validation data set for calibration, using the Hosmer-Lemeshow test, and for discrimination using the receiver-operating characteristic curve analysis. A comparison of the predictive ability of the new score with the current risk scoring methods for prediction of in-hospital mortality will be performed in the overall dataset as well as in the validation dataset using the DeLong test. The improvement of discrimination of the new score will be estimated by calculating the net reclassification index and the integrated discrimination improvement.

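### Calibration of the new mortality score rests on a Hosmer-Lemeshow p-value alone, which gives no size or direction of error and can miss moderate overfitting

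*Protocol*

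**What the plan says.** Protocol section 8.3 (Statistical Analysis) plans a risk score from a random 75/25 split of the cohort. Candidates are screened univariately in the derivation set "to identify predictors of in-hospital mortality". They then pass through stepwise selection in bootstrap samples and a further forward selection on the Akaike information criterion.

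The score is checked in "the validation data set (25.0% of patients"). On calibration the protocol says: "The model will be tested in the validation data set for calibration, using the Hosmer-Lemeshow test". The general significance rule in the same section is: "A p<0.05 will be set for statistical significance".

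No other calibration measure for the score is named. The ROC curve, DeLong test, net reclassification index and integrated discrimination improvement concern discrimination or reclassification. The observed-to-expected ratios later in section 8.3 compare centres and do not validate the score.

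The size of the validation set is not stated and depends on which registry size is used. The synopsis expects "details for more than 10000 patients". Section 8.1 says "it is estimated that the registry will encompass more than 5000 patients in total". Section 8.2 says "a study population of 4000 patients would be enough" for its own question.

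**The concern.** A risk score is used for its absolute predictions, and section 13.1 expects the registry to inform the assessment of operative risk. What matters is how far predicted deaths depart from observed deaths, and in which direction. A Hosmer-Lemeshow p-value answers neither question. It tests a null hypothesis of perfect fit, so a large p-value may mean good fit or too few deaths.

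The likeliest fault in a model built by several rounds of data-driven selection is overfitting: high risks predicted too high and low risks too low. That is a calibration slope below 1. The Hosmer-Lemeshow test spreads its power over ten risk groups instead of aiming at this one departure. An overfitted score could therefore pass the only calibration check named, and the planned output would not show how overfitted it is.

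**Working it through.** The protocol gives no power, precision or tolerance for the validation, so there is no figure to reproduce. The check is a simulation.

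**Inputs from the protocol.** Validation share 25%, significance level 0.05 and outcome in-hospital mortality (section 8.3). Registry size 4000 (section 8.2), 5000 (section 8.1) or 10000 (synopsis). The protocol gives no in-hospital mortality rate. Section 5.1 cites 30-day rates of 16.9% to 18%, and one national database analysis "reported a 30-day mortality of 17" per cent; 17% is used as a proxy.

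**Assumptions not in the protocol.** The predicted logit is normal with mean −1.85 and SD 0.9 (mean risk 16.7%). There are ten risk groups and 10 degrees of freedom, as suits data not used for fitting.

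**Step 1: validation size.**
- 0.25 × 4000 = 1000 patients; 0.17 × 1000 = 170 deaths.
- 0.25 × 5000 = 1250 patients; 0.17 × 1250 ≈ 213 deaths.
- 0.25 × 10000 = 2500 patients; 0.17 × 2500 = 425 deaths.

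**Step 2: what each measure reports.** The Hosmer-Lemeshow statistic is the sum over groups g of (O_g − E_g)² / [E_g(1 − E_g/n_g)]. Squaring removes the direction, and the sum is not on a risk scale. Logistic recalibration fits logit(risk) = a + b × (predicted logit). The slope b is below 1 when the score is overfitted. The intercept a, with b fixed at 1, or the ratio O/E, measures overall over- or under-prediction. Each has a confidence interval.

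**Step 3: detection of a true slope of 0.8 at the 5% level.**

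| Validation patients | Hosmer-Lemeshow | Calibration-slope test |
|---|---|---|
| 1000–1250 | about 22–28% | about 45–57% |
| 2500 | about 50–56% | about 82–84% |

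Hosmer-Lemeshow thus misses this slope in about 72–78% of runs at the smaller sizes and 44–50% at 2500. Under perfect calibration both tests reject in about 5% of runs, so the comparison is fair.

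**Step 4: sensitivity.** With 17% deaths and an AUC of 0.70 to 0.75 (true logit SD 0.775 to 1.025), detection of slope 0.8 at 1000, 1250 and 2500 patients is:
- Hosmer-Lemeshow: 27–37%, 32–46% and 57–76%.
- Slope test: 50–62%, 57–77% and 89–95%.

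The levels move; the ordering does not. Using 8 degrees of freedom raises Hosmer-Lemeshow rejection, but a perfectly calibrated score is then rejected in 10–13% of runs.

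**Step 5: gross error.** At 2500 patients Hosmer-Lemeshow finds a slope of 0.7 in 97–100% of runs and a 20% error in overall risk in 86–99%.

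**Step 6: overall shift under a random split.** Both sets come from one population, so a shift arises mainly from sampling error in the derivation set. With 7500 derivation patients the relative standard error of mean risk is √(0.83 / (0.17 × 7500)) ≈ 2.6%. A 12% over-prediction would be 12 / 2.6 ≈ 4.6 standard errors. With 3000 derivation patients it is √(0.83 / (0.17 × 3000)) ≈ 4.0%, or 3 standard errors.

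**Step 7: what intervals would show.** For a well-calibrated score, with AUC 0.70 to 0.75, the 95% CI half-widths are:

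| Validation patients | Slope | O/E |
|---|---|---|
| 1000 | 0.20–0.24 | about 0.13 |
| 1250 | 0.18–0.22 | about 0.12 |
| 2500 | 0.13–0.15 | about 0.08 |

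Even the slope test has limited power at the smaller sizes. That favours reporting an interval, which shows the uncertainty, over any test alone.

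**The case against.** **Overfitting may be small.** A simulated derivation with 12 true predictors among 30 or 60 candidates, and simple selection at p<0.05 standing in for the planned procedure, gave a mean true slope of 0.96–0.98 (95% range 0.89–1.06) for a registry of 10000. A slope of 0.8 did not occur there. At 4000 the mean was 0.89–0.94, with the lower end of the range about 0.79–0.84. This stands as a limit on the concern. It also means that overfitting near 0.8 is plausible where Hosmer-Lemeshow is weakest.

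**The test is not blind.** A reader might infer that it misses material miscalibration in general. The figures do not support that: at 2500 patients gross error is nearly always found, and a slope of 0.8 is found about half the time or more.

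**Over-prediction.** A reader might also fear a sizeable overall shift. At 2500 patients a 12% over-prediction is found by Hosmer-Lemeshow in only about 30% of runs, against 73–75% by the intercept test. But the random split in section 8.3 makes so large a shift unlikely, so it is not the main ground.

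**No pass rule is written.** The protocol does not say that a non-significant result will be published as good calibration, nor does it rule out a plot or decile table. That reading would be an inference. A statistical analysis plan may also add measures. Even so, the protocol itself chose this method and names no other.

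**Limited weight.** The score is not among the listed objectives or outcomes, and section 14 expects 42 studies. This lowers the priority but does not alter the method point.

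**Conclusion.** The concern holds in moderate form. Hosmer-Lemeshow in the 25% validation set is the only calibration measure the protocol names for the score. That its p-value gives no size or direction, and that non-significance does not show good calibration, depends on no simulation assumption.

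The power figures do rest on assumptions: about 17% mortality taken from 30-day rates, a normal logit with SD 0.9, and no loss of validation patients to missing data. On these, a true slope of 0.8 would go undetected in roughly three of four validation sets at 1000–1250 patients and in about half at 2500. The slope test detects it markedly more often at every size.

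The documents do not support saying that gross miscalibration would be missed at 2500 patients, or that large overall over-prediction is to be expected. The change is worth making before the score is developed; it does not touch the registry's primary objective.

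**What to change.** In section 8.3, make the calibration assessment of the score the following, in the whole validation set:
- the calibration slope with a 95% CI;
- calibration-in-the-large (intercept with slope fixed at 1, or O/E) with a 95% CI;
- a smoothed calibration plot of observed against predicted in-hospital mortality.

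Hosmer-Lemeshow may stay as a descriptive extra, with a statement that a non-significant result will not be read as evidence of good calibration.

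Calibration slopes and smoothed plots by centre should not be added. With the 32 centres of the synopsis, the validation set averages 1000 / 32 ≈ 31 to 2500 / 32 ≈ 78 patients per centre, or about 0.17 × 31 ≈ 5 to 0.17 × 78 ≈ 13 deaths. That is too few for a useful slope or curve.

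The cost is a few more lines of analysis, with no new data.

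### Comparing the new risk score with established scores in the overall dataset re-uses the 75% of patients on whom it was built, so that DeLong test favours the new score and inflates false superiority

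*Protocol*

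**What the plan says.** Protocol section 8.3 (Statistical Analysis) describes how a risk score for in-hospital mortality will be developed. The cohort is split at random, 75% for derivation and 25% for validation. Selection and fitting use the derivation part: "Multiple logistic regression analysis will be then performed using the derivation dataset", and "A stepwise procedure with a bootstrap approach will be used, and 100 samples will be extracted with a size of 70% of the derivation dataset", followed by a forward step based on the Akaike criterion.

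The finished model is assessed in the held-out part: "The model will be tested in the validation data set for calibration", and likewise for discrimination by ROC analysis. The comparison with established scores is handled differently. It "will be performed in the overall dataset as well as in the validation dataset using the DeLong test". The net reclassification index (NRI) and the integrated discrimination improvement (IDI) are also planned, with no dataset named. The section gives no optimism correction for the overall-dataset result and does not say which of the two DeLong comparisons decides.

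**The concern.** The DeLong test treats both scores as fixed before the data were seen. In the validation set this is true of both. In the overall dataset it is true only of the established scores: the new score's covariates and coefficients were chosen to fit three quarters of those patients. Its AUC there includes optimism that its competitors do not have, and the test counts that optimism as evidence of superiority.

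The bias has one direction and carries a p-value. If the two comparisons disagree, nothing in the section prevents the overall-dataset result, which has four times the patients, from being reported as the main one. NRI and IDI would be optimistic in the same way if they were computed there.

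**Working it through.** The protocol gives no AUC, AUC difference or error rate for this comparison, so there is no figure to reproduce. The check was Monte Carlo simulation.

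**Inputs from the protocol**
- 75/25 random split and p<0.05 (section 8.3). Sidedness is not stated. It is taken as two-sided, which leaves 2.5% in favour of the new score.
- Total N: more than 10000 (Synopsis, section 13.3), more than 5000 (section 8.1), 4000 (section 8.2).
- Mortality 17%. Section 5.1 cites 30-day figures of 16.9% to 18%, used here as a proxy for in-hospital death.

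**Sizes** (validation patients = 0.25 × N; deaths = 0.17 × patients)

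| N | Derivation: patients / deaths | Validation: patients / deaths |
|---|---|---|
| 4000 | 3000 / 510 | 1000 / 170 |
| 5000 | 3750 / 638 | 1250 / 213 |
| 10000 | 7500 / 1275 | 2500 / 425 |

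**Assumptions, because the protocol does not give them:** 20, 40 or 80 candidate covariates; true AUC about 0.70 to 0.73; comparator correlated 0.5 to 0.95 with the new score's predictors; either the full model or elimination at p<0.157 as an AIC-like stand-in for the stated algorithm.

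**Main simulation.** A logistic score was fitted on 75% of N. The comparator was built to have exactly the same population AUC in every run, so any finding of superiority is false. A paired DeLong test was run in each dataset and false superiority counted as z > 1.96, with 100 to 400 runs per setting. The ranges run over the correlations 0.5 to 0.95.

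| N | Candidates | Model | Mean AUC gain, overall | False superiority, overall | False superiority, validation |
|---|---|---|---|---|---|
| 4000 | 20 | full | 0.010 | 15-47% | 1.5-2.8% |
| 4000 | 40 | full | 0.020 | 38-85% | 2.5-4.0% |
| 4000 | 80 | full | 0.039 | 91-100% | 0.5-3.5% |
| 10000 | 20 | full | 0.004 | 10-28% | 2.2-3.5% |
| 10000 | 40 | full | 0.008 | 23-73% | 1.8-3.3% |
| 10000 | 80 | full | 0.017 | 63-97% | 3.0-4.5% |
| 4000 | 40 | selected | 0.016-0.017 | 26-69% | 1-4% |
| 10000 | 40 | selected | 0.004-0.006 | 8-44% | 0-2% |

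In the overall dataset the opposite error, new score falsely inferior, occurred in at most 1% of runs. The validation rates agree with 2.5%: with 200 runs the simulation standard error is √(0.025 × 0.975 / 200) = 1.1 percentage points, so two standard errors reach 4.7%.

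**Closer to the stated algorithm.** A second simulation used 100 subsamples of 70%, the stated entry and stay thresholds, the 50% rule, the forward AIC step and a refit. The initial univariate screen was omitted and the selection steps used a linear approximation. The comparator used the same covariates and had equal true AUC. There were 10 true covariates and 120 runs per setting.

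| N | Null covariates | Mean AUC gain, overall | False superiority, overall | False superiority, validation |
|---|---|---|---|---|
| 5000 | 20 | 0.010 | 73% | 2.5% |
| 5000 | 40 | 0.016 | 90% | 2.5% |
| 10000 | 20 | 0.005 | 79% | 2.5% |
| 10000 | 40 | 0.008 | 93% | 0% |

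**Comparator built on separate data.** A third simulation (N = 5000 to 10000, 200 runs per setting) gave 57-92% overall and 2-5.5% in validation. A repeat of that design showed the two scores correlating at 0.91 to 0.98.

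**Why the rate varies so much.** The AUC bias is set mainly by N, the number of candidates and selection. The rejection rate also depends on the correlation between the scores: the closer they are, the smaller the standard error of the AUC difference, and the more readily a small bias reaches significance. The second and third simulations used highly correlated comparators and so lie towards the high end.

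**The case against.** The strongest reply is that the same sentence already plans the sound analysis in the validation set, and that calibration and discrimination are tested there. A reader would see both results. That stands, and it limits the defect to one of two stated tests. It does not remove it, because neither test is named as decisive.

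The reply can add that the bias is small at the planned size. With N = 10000, 40 candidates and AIC-like selection it is about 0.005 in AUC, and false superiority is 8-44%. The established scores are not named, so their correlation with the new score is unknown and the rates near 90% need not apply. This also stands. Even so, the lowest rate found is about three times nominal (8 / 2.5 = 3.2).

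Three stronger readings are tempting, and the protocol does not support them.
- **The test will certainly declare the new score superior.** It will not: the error rate is inflated by an amount that depends on quantities the protocol does not fix.
- **The selection rules add to the bias.** Entry at 0.10 with stay at 0.05 is an odd order, but a covariate with p between the two ends up excluded, so the rule works as the stricter 0.05. The AIC step is looser, admitting a 1-df covariate at P(χ² > 2) = 0.157. Adding it to a core set is a modelling preference, and the held-out set would expose any overfitting. Selection lowered the bias in the main simulation: 23-73% without it and 8-44% with it, at N = 10000 and 40 candidates.
- **The score comparison is a headline product of the registry.** Neither the Synopsis nor section 6.2 lists a risk score among the objectives, and section 14 expects 42 studies.

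**Conclusion.** The concern holds for the overall-dataset comparison. That DeLong test includes the new score's training data and is biased in its favour. Under equal true AUC, false superiority is about 8% to 100% against a nominal 2.5%, roughly 3 to 40 times, with an AUC bias of about 0.004 to 0.04. In the validation set the rate is about 0% to 5.5%.

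The direction follows from the design alone. The size rests on the assumed N, number of candidates, selection procedure and correlation between scores, so it should be quoted as a range. The point on NRI and IDI is conditional, because the section does not name their dataset.

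**What to change.** In section 8.3, state that the decisive comparison with established scores is the DeLong test in the 25% validation set. Alternatively, make it a bootstrap optimism-corrected or cross-validated estimate that repeats the whole modelling procedure, selection included, in each resample. State that NRI and IDI are computed on that same basis. Drop the overall-dataset DeLong test, or report it as descriptive only, with no superiority claim.

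The change is to wording only and can be made before the analyses, which section 8.4 places after 31 December 2025. The cost is precision. The validation set holds about 0.25 × 10000 × 0.17 = 425 deaths if N = 10000, and 170 if N = 4000. With a quarter of the patients, the standard error of an AUC is about √4 = 2 times as large: for an AUC of 0.75 at N = 10000, about 0.014 against 0.007 by the Hanley-McNeil formula. Cross-validation or optimism correction largely recovers this, at the price of more computation.

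### The new mortality score is compared with existing scores in the overall dataset, three quarters of which was used to build it, so that DeLong test is biased towards the new score

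*Protocol*

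**What the plan says.** Protocol section 8.3 (Statistical Analysis) describes a risk score for in-hospital mortality. The cohort is divided at random into "the derivation data set (75.0% of patients) and the validation data set (25.0% of patients". The score is built on the larger part: candidates are screened univariately there, and "Multiple logistic regression analysis will be then performed using the derivation dataset". Selection is by stepwise regression in 100 samples, each 70% of the derivation set, with the rule that "Variables selected in at least 50% of the stepwise procedures will be included in the regression model". Forward steps by the Akaike criterion then add further covariates.

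The score's own performance is checked on the held-out part: "The model will be tested in the validation data set for calibration, using the Hosmer-Lemeshow test", and discrimination is checked there by ROC analysis. The comparison with existing scores is treated differently. It "will be performed in the overall dataset as well as in the validation dataset using the DeLong test". Neither comparison is named as the deciding one, and no correction for optimism is attached to the overall one. The general threshold is "A p<0.05 will be set for statistical significance".

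**The concern.** The overall dataset is the derivation set plus the validation set. In three quarters of it, the new score's variables and coefficients were chosen because they fit those same outcomes. Under this plan the existing scores are not refitted to these patients. One side of a paired comparison carries optimism and the other does not.

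The DeLong test has no allowance for this. Its variance describes the sampling error of two scores fixed before the data were seen, so the extra AUC gained by fitting and selection is counted as a true difference.

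At stake is the claim that the new score discriminates better than current ones. Overfitting alone could produce that claim, and the faulty comparison is the one with four times as many patients, so it will usually look the more convincing.

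**Working it through.** The protocol gives no AUC, power or sample size for this comparison, so there is no stated figure to reproduce. The share of re-used data follows from the split: 75.0% + 25.0% = 100%, so 75% of the overall dataset is derivation data.

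**Inputs from the protocol**
- Cohort size: 4000 (section 8.2, "a study population of 4000 patients would be enough"), more than 5000 (section 8.1), more than 10000 (Synopsis and section 13.3).
- Threshold 0.05 (section 8.3), taken as two-sided because sidedness is not stated. The nominal rate in favour of one named score is then 2.5%.
- Mortality 17%. Section 5.1 cites 30-day mortality of 16.9% to 18%; using this for in-hospital mortality is an assumption.

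**Patients and expected deaths**
- Derivation, 0.75 × N: 3000, 3750 and 7500 patients. At 17% this is 510, 638 and 1275 deaths.
- Validation, 0.25 × N: 1000, 1250 and 2500 patients, or about 170, 213 and 425 deaths.

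**Simulation under the null of equal true AUC**

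Assumptions: 60 candidate covariates, 12 with real effects; selection simplified to a univariate screen at p<0.10 followed by backward elimination at p<0.05; an existing score calibrated to the new score's average out-of-sample AUC. The test statistic is z = (AUC_new − AUC_old) / √Var(AUC_new − AUC_old), with the DeLong variance. The new score is declared better if z > 1.96. There were 400 to 1500 runs per setting.

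| Correlation of scores | N | AUC gain, derivation | AUC gain, validation | AUC gain, overall | New declared better, overall | New declared better, validation |
|---|---|---|---|---|---|---|
| High | 4000 | 0.0151 | 0.0005 | 0.0114 | 78.0% | 3.3% |
| High | 5000 | 0.0122 | 0.0001 | 0.0092 | 79.7% | 3.5% |
| High | 10000 | 0.0057 | −0.0001 | 0.0043 | 77.9% | 4.3% |
| Lower | 4000 | 0.0193 | 0.0016 | 0.0149 | 29.9% | 3.7% |
| Lower | 10000 | 0.0083 | 0.0012 | 0.0065 | 18.5% | 4.0% |

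The overall gain is close to the weighted mean of the two parts. For example, at N=4000 with high correlation, 0.75 × 0.0151 + 0.25 × 0.0005 = 0.0115, against 0.0114 simulated. Nearly all of the overall gain therefore comes from the re-used patients. The overall test never declared the existing score better in any setting; the validation test did so in 1.7% to 3.7% of runs.

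**Other assumptions**
- 45 candidates, 12 real, variables kept if |z| > √2: overall gain 0.006 to 0.023. False superiority was 18% to 58% with score correlation 0.5 to 0.65, and about 90% with highly correlated scores. Validation: 2% to 6%.
- 50 candidates, 12 real, existing score built in the same way on independent data: gain 0.015 at N=4000 and 0.006 at N=10000. False superiority was 93% to 94%. Validation: 1% to 8%.

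**Effect of cohort size.** Optimism shrinks as N grows, but so does the standard error of the paired difference. With highly correlated scores the false-positive rate stayed near 78% to 80% from N=4000 to N=10000; with less correlated scores it fell from 30% to 18.5%. A larger registry does not make the error worse, but within the planned sizes it does not remove it.

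**The case against.** The strongest reply is that a valid test is planned in the same sentence. The validation comparison does not re-use data, calibration and discrimination are checked only there, and a reader who sees both results could notice a gap between them. This stands: the plan is not left without a sound comparison. It does not rescue the overall test, whose p-value remains invalid and which the plan puts on an equal footing with the valid one.

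The second reply concerns size. The protocol gives no number of candidates, does not name the existing scores and does not say how they correlate with the new one, and none of the simulations ran the planned selection procedure exactly. That also stands. The rates are illustrative and vary widely between settings. The spurious gain is small as an AUC difference, about 0.004 to 0.007 at N=10000 in the tabulated runs. The direction of the bias does not depend on these choices.

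Third, because the existing scores are not named, it cannot be checked that none was developed on some of the same patients. A score that was would carry optimism of its own, but that would be a further reason not to rely on the overall comparison.

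Finally, the score is one product among the 42 studies expected in section 14 and is not a listed outcome. That limits the consequence to the risk-score work.

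**Conclusion.** The overall-dataset comparison is wrong as written. It tests the new score largely on the patients used to build it and reports a p-value that does not allow for this. The bias favours the new score by design, which is not the same as guaranteeing a significant result.

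Across the assumptions tried (45 to 60 candidates, 12 real, about 17% mortality, N from 4000 to 10000, equal true AUCs), the spurious AUC gain was 0.004 to 0.023. A false finding of superiority occurred in about 18% to 94% of runs against a nominal 2.5%, with the high end for highly correlated scores. The validation comparison stayed at 1% to 8% and is free of this fault. Because that valid test is already planned, the point should be corrected but does not undermine the registry as a whole.

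**What to change.** In Protocol section 8.3 (Statistical Analysis), strike the overall dataset from the sentence on the DeLong test, so that the new score is compared with existing scores in the validation dataset only.

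If an all-patient figure is wanted, report the AUC difference corrected for optimism by bootstrap or cross-validation. The whole building procedure (univariate screen, resampled stepwise selection, Akaike forward steps, refit) must be repeated within each resample. The apparent difference and its DeLong p-value should not be used.

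The following sentence, "The improvement of discrimination of the new score will be estimated by calculating the net reclassification index and the integrated discrimination improvement", names no dataset. When the text is edited, tie these two measures to the validation dataset as well, or the same optimism can enter there.

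The change is one phrase. Its cost is precision: with a quarter of the patients (1000 to 2500), the standard error is about √4 = 2 times as large, so the interval is roughly twice as wide. The resampling alternative uses all patients and costs computing time.
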